5.6. Potential Risk/Benefit Analysis

5.6.1. Potential Study Risks

5.6.1.1. Describe and assess all of the following risks that may be associated with the research:

Physical

To minimize the chance for serious and unexpected adverse events, study participants will be screened through exclusion criteria for any health conditions that may be exacerbated by participating in a physical activity study. The program will use a gradual increase in physical activity during the first month that should pose little health risk to participants. Participants are given guidance on when to seek medical attention and a reporting protocol is in place to capture any changes in symptoms with physical activity.

5.6.1.3. Psychological: Not applicable.

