5.1. Study Design

5.1.1. Describe in detail the experimental design, i.e. from recruitment procedures to study closure.

Design. Forty patients will be enrolled in the proposed work. Participants will be randomly assigned to one of two groups for the 12-week intervention period: (1) usual care; or (2) TEC strategies with enrollment in a weekly regret lottery.

Sample and Setting. The sample will be comprised of patients receiving care at the Corporal Michael Cresenz VA Medical Center (CMCVAMC) in Philadelphia as well as at the Pain-focused Patient Aligned Care Team (P-PACT). This primary care clinic was instituted to provide comprehensive, evidence-based care to patients with chronic non-malignant pain and on opioid therapy. Patients referred to the program are those identified as high-risk related to being on high dose opioid therapy; on combined opioid/benzodiazepine therapy; and/or having a history of substance abuse. A key component of the P-PACT program is improving mobility amongst patients using modalities available through the VA, including physical therapy, yoga and tai chi, which have an evidence base to improve pain, sleep, cognitive and physical function as well as decrease medication use.

Inclusion Criteria	Exclusion Criteria

• Chronic non-malignant pain• High dose opioid therapy• Possession of activated cell phone with text messaging capabilities• Willingness to comply with study requirements	
• Pain of malignant origin• Sensory impairments precluding use of text messaging and activity tracker• Physical disability precluding improvements in physical activity

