Procedures. Eligible patients will be offered participation in this pilot study. The enrollment goal of 40 patients was chosen based on feasibility given the time-frame. Following informed consent, participants will be randomly assigned to one of the two study arms. All participants will be provided individual activity regimens, and be offered physical therapy, yoga, or tai-chi classes at the CMCVAMC. The activity goal will be participation in their activity regimen or classes at least twice per week, a frequency used in other studies promoting activity for chronic pain. Participants will self-report their activity, pain severity, functionality, and opioid use monthly via questionnaire and pill counts. Additionally, all participants will be provided an activity tracker to measure steps taken and instructed on use and data upload procedures. Upon the completion of their 12-week participation, participants are asked to complete an in-person exit survey answering questions about their experience in the study, the use of the FitBit activity watches, as well as the use of the FitBit application.

Those receiving the TEC-linked intervention will be familiarized with the text messaging process and the measures that will be administered via this technology. TEC will consist of a daily personalized text message from a dedicated research assistant reminding the patient to engage in their prescribed physical activity for the day. A second text message at the end of the day will direct the patient to return activity participation, pain severity, functionality, and opioid use data, and upload activity tracker data to the Way to Health (WTH) platform. The behavioral incentive provides the opportunity for subjects who meet their weekly activity goals to enter a lottery to receive either a small (\$30) or large (\$100) financial incentive. The lottery is structured such that subjects have an 18% chance/week of winning the small prize, and a 1% chance of winning the large prize. For those not meeting goals, they will be informed what they would have won had they met their goal. This design has been used in similar studies, with evidence showing the desire to avoid regret can be motivating.

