5.4.5.2. Exclusion Criteria

1) Pain of malignant origin; 2) Sensory impairments precluding use of text messaging and activity tracker; or 3) Physical disability precluding improvements in physical activity.

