5.6.1.6. Loss of Confidentiality

A potential risk of this study is a breach of participant confidentiality. We will minimize this risk by using secure data methods as described previously. Names and addresses will be stored in encrypted databases. These data will be viewable only by the respective participants and the study coordinator. All other members of the research team will be able to view only participant ID numbers. There will be no functionality in the web application to export a dataset with identifiable information. Even the study arms will be identified by code letters until both the statistician and PI agree that analysis is complete.

5.6.1.7. **Other, e.g. radiation, placebo, washout of medications:** Not applicable
5.6.1.8. **Assess the likelihood and seriousness of such risks.:** Not applicable

5.6.2. Include a description of how anticipated risk will be minimized and include an analysis of risk vs. potential benefit.

Anticipated risks of this study should be minimal and the risk/benefit ratio is very favorable. To minimize the chance for serious and unexpected adverse events, study participants will be screened through exclusion criteria for any health conditions that may be exacerbated by participating in this study. We have previously outlined the procedures that will be used to prevent a breach of participant data.

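### Sections 5.6.1.1 and 5.6.2 promise an exclusion screen for any condition that participation may worsen, but neither exclusion list contains a criterion that delivers it

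*Combined protocol and SAP*

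**What the plan says.** Section 5.6.1.1, on physical risk, states that "study participants will be screened through exclusion criteria for any health conditions that may be exacerbated by participating in a physical activity study". Section 5.6.2, on risk minimisation, says again that participants are "screened through exclusion criteria for any health conditions that may be exacerbated by participating in this study". It places this beside the conclusion "Anticipated risks of this study should be minimal and the risk/benefit ratio is very favorable". The only other measure 5.6.2 mentions is protection of participant data.

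The exclusion criteria appear in full in two places, the table in 5.1.1 and the list in 5.4.5.2. Each has three items: malignant pain, sensory impairment that prevents use of texts and the tracker, and "Physical disability precluding improvements in physical activity". Section 5.1.4 repeats the last two when asked about safeguards for vulnerable groups.

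Activity is part of the plan in both arms: "All participants will be provided individual activity regimens", with a goal of at least two sessions a week.

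**The concern.** The risk section describes a screen that works through the exclusion criteria and covers any condition that participation might exacerbate. A reader who turns to the criteria finds nothing of that breadth. Staff who apply the protocol exactly would enrol a patient with a condition that exertion could worsen, provided the patient met the inclusion criteria and none of the three exclusions applied.

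Two things are at stake: the safety of such a patient, and the accuracy of what the IRB is told. In 5.6.2 this screen is the only physical-risk measure offered in support of a favourable risk/benefit judgement. The form's item 5.6.1.8, "Assess the likelihood and seriousness of such risks", is answered as not applicable, so no separate assessment of risk stands behind that judgement.

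**Working it through.** There is no figure to reproduce. The check sets the claim against every place where eligibility or clearance is described.

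1. **The claim (5.6.1.1 and 5.6.2).** The means is the exclusion criteria. The scope is any health condition that participation may exacerbate. Section 5.6.2 speaks of the study and 5.6.1.1 of a physical activity study. Since the study promotes activity, the two say the same thing.

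2. **Exclusions 1 and 2 (5.1.1 table, 5.4.5.2).** Malignant pain defines the pain population. Sensory impairment concerns use of the technology. Neither is a screen for whether activity is safe.

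3. **Exclusion 3, "Physical disability precluding improvements in physical activity".** This is the nearest item. Its test is whether a disability prevents improvement. Some patients for whom activity is inadvisable would meet it. A patient who is able to do more, but has a condition that doing more could aggravate, would not. It is also limited to physical disability, whereas the claim extends to all health conditions.

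4. **Inclusion criteria (5.4.5.1, also 5.1.3).** The five items are adult age, chronic non-malignant pain, high-dose opioid therapy, a phone that can receive texts, and willingness to comply. The 5.1.1 table lists the last four. None concerns fitness for activity.

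5. **Enrolment steps (5.2.3).** After consent, a visit covers eligibility and baseline surveys. No clinical clearance is written. The text on first contact is partly removed, so a clinician may well be involved there, but no written step uses that contact to screen for exercise safety.

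6. **Referral to the pain clinic (5.1.1).** "Patients referred to the program are those identified as high-risk related to being on high dose opioid therapy"; combined opioid and benzodiazepine therapy and a history of substance abuse are the other grounds. None of these is an exercise-safety filter, and recruitment also draws on the wider medical center.

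Result: the claim is made twice. No criterion of matching scope appears in either exclusion list or among the inclusion criteria.

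**The case against.** The best defence is that 5.6 refers loosely to the existing list. Section 5.1.4 offers the disability exclusion in answer to a question about safeguards, so the authors evidently regard it as protective. On that view the fault is an overbroad word, not an absent safeguard. This stands in part: the item does some protective work, and the point should not be put as if there were no screening at all. It still does not reach the patient described in step 3.

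Second, improving mobility through physical therapy, yoga and tai chi is already a key part of the pain clinic's care, so the added research risk for those patients is smaller than it looks. That stands too, with two limits: not all recruits need come from that clinic, and the protocol does not say who sets the individual regimens.

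Third, other safeguards exist. Activity rises gradually in the first month, participants are told when to seek care, a reporting protocol captures symptom changes with activity, and under 5.7.1.2 the PI reviews reported problems and can decide that a participant should stop. These make serious harm less likely. They act after entry, so they do not replace a screen at entry.

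A reader might also infer more than the documents support:

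- **That all 40 participants are exposed to the gap.** All receive a regimen, but the gap matters only for someone who passes the three exclusions and has a condition that graded activity would worsen. The documents give no means of counting such people.
- **That 5.1.1 leaves the order of eligibility and randomisation open.** It does say "Following informed consent, participants will be randomly assigned to one of the two study arms", but the same paragraph opens by restricting the offer of participation to eligible patients. The real difficulty is that 5.2.3 puts the eligibility visit after consent, so the two sections need reconciling.
- **That each extra screen failure costs a known amount of recruitment time.** Forty patients over months 4 to 7 is 40/4 = 10 a month, or about three days each. Reading that as a cost assumes that the supply of patients limits enrolment, and no referral volume or screen-failure rate is given.

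**Conclusion.** Wrong as written, minor severity. The screening statement in 5.6.1.1 and 5.6.2 is broader than the criteria meant to carry it out, and a protocol followed to the letter would not deliver the stated screen.

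The size of the problem cannot be expressed as a number of patients or a probability of harm. Absolute risk is probably low, for the reasons given under the objection. No outcome, comparison or analysis is affected.

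The conclusion assumes that the eligibility text is complete (both lists agree, and nothing in them appears to be removed) and that no clearance step exists in a document outside this one. If clinicians already screen informally, patients may be protected in practice, but the protocol would still attribute that protection to criteria that do not contain it.

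**What to change.** Add one exclusion to the 5.1.1 table and to 5.4.5.2: *any condition for which a study or treating clinician judges the planned activity unsafe*. Have a clinician already on the team apply it at the eligibility assessment; the pain clinic's medical director is one candidate. Which conditions count is for the clinicians to decide.

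State that the check is confirmed before randomisation, and align 5.1.1 with 5.2.3 on whether eligibility is settled before or after consent. Allow clearance on a modified regimen, so that a patient who can safely do a lighter programme is not lost. If the clinician will consult records, the unticked chart-review box in 5.1.2 needs updating. The stored data in 5.10.1 include a problem list, but its source is not stated.

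If this screen was never intended, narrow the wording in 5.6.1.1 and 5.6.2 to the three listed criteria. That corrects the record but adds no protection.

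The cost is one line in two places, a short clinical check at an assessment already planned, and possibly some extra screen failures, whose number the documents do not allow one to estimate.

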5.6.1.4. Social/Economic: Not applicable

5.6.1.5. Legal: Not applicable.

5.6.1.6. Loss of Confidentiality

A potential risk of this study is a breach of participant confidentiality. We will minimize this risk by using secure data methods as described previously. Names and addresses will be stored in encrypted databases. These data will be viewable only by the respective participants and the study coordinator. All other members of the research team will be able to view only participant ID numbers. There will be no functionality in the web application to export a dataset with identifiable information. Even the study arms will be identified by code letters until both the statistician and PI agree that analysis is complete.

5.6.1.7. **Other, e.g. radiation, placebo, washout of medications:** Not applicable
5.6.1.8. **Assess the likelihood and seriousness of such risks.:** Not applicable

5.6.2. Include a description of how anticipated risk will be minimized and include an analysis of risk vs. potential benefit.

Anticipated risks of this study should be minimal and the risk/benefit ratio is very favorable. To minimize the chance for serious and unexpected adverse events, study participants will be screened through exclusion criteria for any health conditions that may be exacerbated by participating in this study. We have previously outlined the procedures that will be used to prevent a breach of participant data.

5.6.3. Potential Study Benefits

5.6.3.1. **Indicate potential benefits to be gained by the individual subjects, as well as benefit(s) that may accrue to society in general as a result of the planned work. If the subject will not receive any direct benefit, this fact must be stated here and in the consent form.**

Through participation in this study, each participant will have the potential to increase physical activity which could improve their health and reduce their opioid use. If this approach is effective, it could have tremendous benefits for society if adopted on a wide scale to help individuals. It is expected that other people will gain knowledge from this study and that participation could help understand how to effectively motivate individuals to change behavior. Participants may also receive no benefit from their participation in the study.

5.6.4. Alternative Treatments Outside the Study

5.6.4.1. **Describe alternatives available to the subject outside the research context. If there are no such alternatives, state that the alternative is not to participate in the research study.**

The alternative is not to participate in the research study.

5.7. Data Monitoring

5.7.1. **Will a Data and Safety Monitoring Board (DSMB) or Data Monitoring Committee (DMC) oversee the project? No**

5.7.1.1. **If yes, provide contact information for the DSMB or DMC representative.**

5.7.1.2. **If no, describe the data and safety monitoring plan to be followed.**

The Principal Investigator will be responsible for monitoring the study. All participants will be given anticipatory guidance on when to seek medical attention. In addition, participants will be asked to report to the study team any injuries or medical care that they feel resulted from participation in the study. They can either present in person, call the study team or send an email. The research coordinator will call the participant to collect information regarding the issue and then the PI will review and determine whether it is ok to proceed, further investigation is needed, or the participant should stop the study. For this study, there will be no stopping rules or endpoints and thus no planned interim analyses.

5.8. Reporting of Protocol Deviations, Adverse Events (AEs), Serious Adverse Events (SAEs), Breaches of Confidentiality, Unanticipated Adverse Device Effects (UADEs), and Unanticipated/Unexpected Problems

5.8.1. **Include procedures for reporting these events to the CMCVAMC IRB and sponsor.**

Standard protocol will be followed for any events including reporting to the CMCVAMC IRB within 5 business days of discovery. We will use the CMCVAMC serious-adverse event form for reporting SAEs, UADEs, and any other unanticipated/unexpected problems. We will also use the CMCVAMC Protocol

Deviation form for reporting any protocol deviations. Any true adverse events will be reported immediately.

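### The described adverse-event route is participant-initiated and filtered by the participant's own view of cause, narrower than the capture the risk section promises, so events may be missed, possibly unequally by arm

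*Combined protocol and SAP*

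**What the plan says.** Section 5.6.1.1 (physical risks) states that "a reporting protocol is in place to capture any changes in symptoms with physical activity". It sets no condition on what the participant believes about cause.

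Section 5.7.1.2 (data and safety monitoring plan) describes the process: "participants will be asked to report to the study team any injuries or medical care that they feel resulted from participation in the study". On the means of reporting it says: "They can either present in person, call the study team or send an email". Staff act after that: "The research coordinator will call the participant to collect information regarding the issue". The principal investigator then reviews the issue and decides whether the participant continues, needs further investigation or stops. Section 5.7 also states that there is no monitoring board, no stopping rule and no interim analysis.

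Section 5.8.1 covers onward reporting: "Standard protocol will be followed for any events including reporting to the CMCVAMC IRB within 5 business days of discovery", and "Any true adverse events will be reported immediately". It does not say how events come to be discovered, or what makes an adverse event a true one.

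Section 5.1.1 sets the scheduled contacts. All participants report activity, pain, function and opioid use monthly. In the intervention arm, "TEC will consist of a daily personalized text message from a dedicated research assistant", and then "A second text message at the end of the day will direct the patient to return activity participation, pain severity", together with function, opioid use and tracker data. Both arms receive activity regimens and the offer of classes.

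**The concern.** The two safety statements differ in scope. One promises capture of any symptom change with activity. The other depends on the participant making contact, and on the participant having already decided that the study was the cause. A symptom change that is neither an injury nor a reason for medical care falls outside the wording of the second statement altogether.

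Self-attribution is a weak filter in this population. Everyone enrolled has chronic pain, so a flare or strain brought on by the activity regimen can easily be put down to the existing condition. Such an event need not be reported, and the principal investigator's review is triggered by reports. At stake are the oversight of individual participants and the truth of any later statement that the programme was well tolerated.

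**Working it through.** The plan states no adverse-event rate, capture rate or safety calculation, so there is no figure to reproduce. The check is a comparison of sections, followed by arithmetic on assumed values to show what can and cannot be concluded.

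**1. Is another route described?**

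- Monthly self-report (5.1.1): activity, pain severity, function and opioid use. No adverse-event item is listed.
- Daily texts, intervention arm (5.1.1): a reminder in one, and in the other a request for the same four items plus tracker data. No adverse-event item is listed.
- Measures table (5.1.1): pain, function, opioid use, activity, PROMIS-29 and PHQ9. No adverse-event item is listed.
- Research-methods checklist (5.1.2): chart review, interviews and telephone survey are unticked. Section 5.10.1 does mention stored responses from follow-up interviews or surveys, but not their content.
- Exit survey (end of document): questions on technology, with one open comment box. Responses are described as anonymous, so an injury mentioned there might not be traceable to a participant.
- Section 5.8.1: onward reporting only.

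The route in 5.7.1.2 is therefore the only one described.

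**2. How does contact differ by arm?**

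- Intervention arm: 2 texts × 7 days × 12 weeks = 168 texts, of which 7 × 12 = 84 ask for data.
- All participants: about 3 monthly questionnaires in 12 weeks.

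**3. What could under-capture do?** The inputs are 20 participants per arm (5.2.1) and *assumed* event risks and capture fractions, none of which are in the documents.

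Expected recorded participants per arm = 20 × true risk × capture. With the same true risk of 20% in both arms, 20 × 0.20 = 4 participants per arm have an event.

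| Capture, intervention / usual care | Recorded, intervention / usual care | Apparent difference | Missed, of 8 |
|---|---|---|---|
| 80% / 80% | 3.2 / 3.2 | 0 points | 1.6 |
| 80% / 50% | 3.2 / 2.0 | +6 points | 2.8 |
| 50% / 80% | 2.0 / 3.2 | −6 points | 2.8 |
| 90% / 30% | 3.6 / 1.2 | +12 points | 3.2 |
| 30% / 90% | 1.2 / 3.6 | −12 points | 3.2 |

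Over true risks of 10% to 40%, the unequal pairs give an apparent difference of 3 points (0.10 × 0.30) to 24 points (0.40 × 0.60), in either direction. With equal capture it is zero. The sign and size come entirely from the assumed capture fractions.

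**4. What would a clean safety record mean?** If none of 20 participants in an arm has a recorded event, the one-sided 95% upper bound on the recorded risk is 1 − 0.05^(1/20) = 13.9%. Dividing by the capture fraction gives the bound on the true risk: 13.9% with full capture, 13.9/0.8 = 17.4% with 80%, and 13.9/0.5 = 27.8% with 50%. The capture fractions are again assumed.

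**The case against.** The strongest reply is that the gap is inferred from silence. Section 5.6.1.1 says that a protocol exists, 5.8.1 refers to a standard protocol, and reporting instructions may stand in consent pages that are not part of the text available for review. Pain and function are collected monthly, with PROMIS-29 and PHQ9 also listed as monthly, so some symptom change is recorded without any attribution by the participant. This stands in part. It rules out saying that unattributed events *will* be lost. It does not remove the difference in scope between the two sections, and a pain score is not described as a trigger for safety review.

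A reader might go further and infer that events will be missed unequally, with the intervention arm looking worse because it has more contact. The documents do not support that. The reporting instruction and its three routes are the same for everyone, the extra texts list no adverse-event item, and both arms are given activity regimens. More contact could raise reporting. The lottery for meeting activity goals, open only to the intervention arm, could discourage it. Neither effect is stated.

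A reader might also fear a biased trial result. Section 9.2 compares pain, function, opioid use and activity between arms. It plans no adverse-event comparison, so the primary outcomes are untouched.

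Finally, a cause-neutral question put to a high-risk chronic-pain population will bring in unrelated events, and 5.8.1 sends any events to the IRB. That objection stands, and it is why the fix includes a definition.

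**Conclusion.** The concern holds in a limited form. The described route is narrower than the capture promised in 5.6.1.1, and no scheduled contact is shown to ask about adverse events. Events may be missed, possibly unequally by arm. The first risk follows from the wording of 5.7.1.2 together with the absence of any described alternative. The second is only a possibility, and its direction and size cannot be determined from the documents.

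The number of events lost cannot be estimated. The figures above illustrate how far an incomplete count could mislead. The consequence is for participant oversight and for the safety description, not for the efficacy analysis. The conclusion assumes that no fuller protocol exists outside the text. If one does, describing it would answer part of the point. The change is worth making before enrolment because it is cheap and improves on the stated method.

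**What to change.** - Reconcile 5.6.1.1 with 5.7.1.2, and describe the reporting protocol that 5.6.1.1 refers to.
- Add one fixed question to the monthly questionnaire that both arms already complete: any injury, medical care or symptom change since the last contact, whatever the cause.
- Define in 5.8 what counts as an adverse event for reporting, including what is meant by a true one.
- Have the principal investigator, not the participant, assess relatedness.
- Keep spontaneous reporting, but tabulate solicited events by arm separately from spontaneous ones, so that any contact-driven difference stays out of the solicited counts.

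The cost is one item asked about 3 times of 40 people, or about 120 answers (3 × 40), and more unrelated events for the principal investigator to review. The definition limits how many of those go on to the IRB.
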